6.2.2.6 FACT – ES survey

The current standard of care in patients with increased risk of developing breast cancer is anti-estrogen therapy. The FACT-ES score has been validated in patients receiving endocrine therapy. We are using

the FACT-ES score at baseline, 6 months and 1 year so that we can historically compare the side effects in patients on hydroxytyrosol to known endocrine side effects.

6.2.2.7 Breast MRI

Breast MRI images will be collected if available and are not a required test for study participation. The images available will be used to calculate MRI breast density. The axial view T1-weighted images without fat suppression will be used for the analysis of breast density in this study. The images will be acquired using a 2D turbo spin-echo pulse sequence with TR=800 ms, TE=8.6 ms, flip angle=90°, matrix size=480x480, FOV=31–38 cm, and slice thickness=2 mm. The breast and fibroglandular tissue segmentation will be performed using a modified published method. [31-33] Before the segmentation, the operator will view the whole axial T1W images dataset and determined the superior and inferior boundaries of the breast (the beginning and ending slices) by comparing the thickness of breast fat with the body fat. The breast segmentation procedures consisted of: 1) Perform an initial horizontal line cut along the posterior margin of each individual subject's sternum to exclude thoracic region. 2) Apply Fuzzy-C-Means (FCM) clustering and b-spline curve fitting to obtain the breast-chest boundary. 3) A bias field correction method based on nonparametric nonuniformity normalization (N3) and adaptive FCM algorithm [33] will be used to remove the strong intensity non-uniformity for segmentation of fibroglandular tissue and fatty tissue. 4) Apply dynamic searching to exclude the skin along the breast boundary. 5) The standard FCM algorithm is applied to classify all pixels on the image. The default setting is to use a total of 6 clusters, 3 for fibroglandular tissue and 3 for fatty tissues. After completing the segmentation processes in all image slices, the quantitative breast volume, fibroglandular tissue volume, and the percent density (calculated as the ratio of the fibroglandular tissue volume over the breast volume x100%), will be calculated.

6.2.2.8 Criteria for Removal from Protocol Treatment

- a. Evidence of any cancer at any time, including DCIS. If the pathologic review of the baseline core needle breast biopsy confirms invasive breast cancer, the participant must be removed from protocol treatment.
- b. Unacceptable toxicity (as defined in Section 8.0).
- c. A participant who becomes pregnant while on treatment will be removed from protocol treatment since hormonal changes affect mammographic density.
- d. Delay of study intervention > 12 consecutive weeks due to any reason.
- e. Completion of twelve months of study intervention.
- f. The participant may withdraw from the study at any time for any reason.
- g. All reasons for discontinuation of the intervention must be documented in the Off Treatment Notice – Prevention Studies.
8. All participants will be followed for 13 months after registration. After 13 months, no further follow-up is required.
9. Non-compliance with study drug.

6.2.2.9 Withdrawal from Protocol Treatment

Follow-up visits will continue even if the participant goes off study intervention early unless there is a withdrawal of consent.

7 Visit schedule and assessments

7.1 Study flow and visit schedule

Table 7-1 Visit evaluation schedule

Required Studies	Prestudy Evaluation	Day 1	Month 1-2 (Day 30 to 60)	Month 3 (day 90) ¹	Month 6 (day 180) ¹	Month 9 (day 270) ¹	Month 12 (day 360) ¹	Month 13 (day 390) ¹
Clinic Visit								
Breast Cancer Risk Assessment ²	X							
Baseline and Pre-existing conditions	X							
History and Physical Exam ¹³	X			X	X		X	
Height and Weight	X						X	
Vital Signs	X			X	X		X	
Performance Status	X						X	
Toxicity Notation ³				X	X		X	X ¹²
Review of Intake Calendar ⁴				X	X		X	
Laboratory								
Serum liver function tests	X			X	X		X	
Serum lipid panel (fasting)	X			X	X		X	
PT/PTT/INR ⁵	X						X	
FSH (if necessary) ⁶								
CBC and CMP	X			X	X		X	
Serum Pregnancy ¹⁴	X							
Radiographs								
Bilateral Mammogram ⁷	X						X	
Bilateral Breast MRI image collection ⁷	X						X	
Bone Density ⁸	X						X ⁸	
Procedures								

Random core biopsy ⁹	X						X	
Intervention								
Dispense study drug ¹⁰		X			X			
Count Pills				X	X		X	
Questionnaire ¹¹	X				X		X	

1. Followup visits can occur (+/- 14 days for each assessment) to allow flexibility in scheduling. Follow-up visits will continue even if the participant goes off study intervention early unless there is a withdrawal of consent.
2. Risk assessment using Gail risk model if no known history of DCIS or LCIS and no deleterious mutation in BRCA 1 or 2, PTEN or P53
3. On months 3, 6, 12 (Days 90, 180, 360 (+/- 14 days for each assessment)) adverse events will be noted
4. On months 3, 6, and 12 (90, 180, 360 +/- 14 days for each assessment), participants will be seen at the study sites to review the intake calendar which will document drug compliance and date of last menses.
5. PT/PTT/INR required if the patient has been on anticoagulation therapy within 7 days prior to breast core biopsy.
6. FSH only to be performed if menopausal status needs to be determined (e.g. in patient with hysterectomy with at least one ovary intact – see section 7.2.2)
7. Mammogram within 90 days of registration. Imaging to be done prior to breast biopsy. Bilateral Breast MRI images to be collected if conducted within 90 days of registration at baseline End of treatment Breast MRI images to be collected if available.
8. This test information will be collected if available. Bone density not to be ordered specifically for the study..
9. The random core needle biopsy is mandatory for study participation. All new patients on the study will undergo biopsy before and after the study drug. No attempt will be made to have the patients already on the study to undergo mandatory biopsy. All imaging is to be done prior to breast biopsy. If a patient is scheduled for a breast biopsy or surgery, tissue can be collected at that time.
10. A six month supply of the study drug will be dispensed at Day 1 visit and at 6 months. Compliance to be verified via pill count and pill diary.
11. The Fact ES questionnaire will be given at baseline, 6 months and at 12 months
12. Phone call to assess adverse events.
13. Physical exam to include abdominal circumference at baseline, 3, 6 and 12 months
14. Serum pregnancy test if premenopausal and has not had tubal ligation.

7.2 Assessment types

Followup visits can occur (+/- 14 days for each assessment) to allow flexibility in scheduling. Follow-up visits will continue even if the participant goes off study intervention early. Risk assessment using Gail risk model if no known history of DCIS or LCIS and no deleterious mutation in BRCA 1 or 2, PTEN or P53. On months 3, 6, and 12 and 13 (Days 90, 180, 360 and 390 (+/- 14 days for each assessment)) adverse events will be noted. On months 3, 6, and 12 (90, 180, 360 +/- 14 days for each assessment), participants will be seen at the study sites to review the intake calendar which will document drug compliance and date of last menses. PT/PTT/INR required if the patient has been on anticoagulation during the past 7 days. FSH only to be performed if menopausal status needs to be determined (e.g. in patient with hysterectomy with at least one ovary intact). Mammogram within 90 days of registration. Bilateral Breast MRI will not be performed specifically for this study but if the images available within the past 90 days, they will be collected. Bone density not to be ordered specifically for the study and if not available does not exclude the patient from participating. The random core needle biopsy is mandatory for study participation. A six month supply of the study drug will be dispensed at Day 1 and at 6 months. The Fact ES questionnaire will be given at baseline, 6 months and at 12 months.

7.2.1 Pregnancy and assessments of fertility

Pregnancy testing is required at screening for premenopausal patients that have not had tubal ligation or whenever pregnancy is suspected. Serum pregnancy testing should be performed at screening

7.2.2 Determination of Menopausal Status

The following criteria will be used to define *postmenopausal*:

- Age 56 or older with no spontaneous menses for at least 12 months prior to study entry; **or**
- Age 55 or younger with no spontaneous menses for at least 12 months prior to study entry (e.g., spontaneous or secondary to hysterectomy) **and** with a documented estradiol level in the postmenopausal range according to local institutional/laboratory standard; **or**
- Documented bilateral oophorectomy.

Women failing to meet one of these criteria will be classified as *pre-menopausal*.

7.2.2 Drug levels and pharmacokinetic assessments N/A

8 Safety monitoring and reporting

Information about all adverse events, whether volunteered by the subject, discovered by investigator questioning, or detected through physical examination, laboratory test or other means, will be collected and recorded and followed as appropriate.

8.1 Adverse events

8.1.1 Definitions and reporting

Adverse events that begin or worsen after informed consent should be recorded in the Adverse Events CRF. Conditions that were already present at the time of informed consent should be recorded in the Medical History page of the patient's CRF. Adverse event monitoring should be continued for at least 30 days (or 5 half-lives, whichever is longer) following the last dose of study treatment. Adverse events

(including lab abnormalities that constitute AEs) should be described using a diagnosis whenever possible, rather than individual underlying signs and symptoms. When a clear diagnosis cannot be identified, each sign or symptom should be reported as a separate Adverse Event.

The occurrence of adverse events should be sought by non-directive questioning of the patient at each visit during the study. Adverse events also may be detected when they are volunteered by the patient during or between visits or through physical examination, laboratory test, or other assessments. As far as possible, each adverse event should be evaluated to determine:

1. The severity grade (CTCAE Grade 1-4)
2. Its duration (Start and end dates or if continuing at the Safety Follow-up Visit)
3. Its relationship to the study treatment (Reasonable possibility that AE is related: No, Yes)
4. Action taken with respect to study or investigational treatment (none, dose adjusted, temporarily interrupted, permanently discontinued, hospitalized, unknown, not applicable)
5. Whether medication or therapy was given (no concomitant medication/non-drug therapy, concomitant medication/non-drug therapy)
6. Outcome (not recovered/not resolved, recovered/resolved, recovering/resolving, recovered/resolved with sequelae, fatal, unknown)
7. Whether it is serious, where a serious adverse event (SAE) is defined as in Section 8.2.1

All adverse events should be treated appropriately. Such treatment may include changes in study drug treatment including possible interruption or discontinuation, starting or stopping concomitant treatments, changes in the frequency or nature of assessments, hospitalization, or any other medically required intervention. Once an adverse event is detected, it should be followed until its resolution, and assessment should be made at each visit (or more frequently, if necessary) of any changes in severity, the suspected relationship to the study drug, the interventions required to treat it, and the outcome.

Information about common side effects already known about the investigational drug can be found in the [\[Investigators' Brochure\]](#). This information should be included in the patient informed consent and should be discussed with the patient during the study as needed.

Adverse event monitoring should be continued for at least 30 days following the last dose of study treatment

8.1.2 Laboratory test abnormalities

Laboratory abnormalities that constitute an Adverse event in their own right (are considered clinically significant, induce clinical signs or symptoms, require concomitant therapy or require changes in study treatment), should be recorded on the Adverse Events CRF. Whenever possible, a diagnosis, rather than a symptom should be provided (e.g. anemia instead of low hemoglobin). Laboratory abnormalities that meet the criteria for Adverse Events should be followed until they have returned to normal or an adequate explanation of the abnormality is found. When an abnormal laboratory or test result corresponds to a sign/symptom of an already reported adverse event, it is not necessary to separately record the lab/test result as an additional event.

Laboratory abnormalities, that do not meet the definition of an adverse event, should not be reported as adverse events. A Grade 3 or 4 event (severe) as per CTCAE does not automatically indicate a SAE unless it meets the definition of serious as defined below and/or as per investigator's discretion. A dose hold or medication for the lab abnormality may be required by the protocol and is still, by definition, an adverse event.

8.2 Serious Adverse Events

8.2.1 Definitions

A serious adverse event is an undesirable sign, symptom or medical condition which:

- is fatal or life-threatening
- results in persistent or significant disability/incapacity
- constitutes a congenital anomaly/birth defect
- requires inpatient hospitalization or prolongation of existing hospitalization, unless hospitalization is for:
 - routine treatment or monitoring of the studied indication, not associated with any deterioration in condition (specify what this includes)
 - elective or pre-planned treatment for a pre-existing condition that is unrelated to the indication under study and has not worsened since the start of study drug
 - treatment on an emergency outpatient basis for an event not fulfilling any of the definitions of a SAE given above and not resulting in hospital admission
 - social reasons and respite care in the absence of any deterioration in the patient's general condition
- is medically significant, i.e., defined as an event that jeopardizes the patient or may require medical or surgical intervention to prevent one of the outcomes listed above

8.2.2 Reporting

The principal investigator has the obligation to report all serious adverse events to the FDA, and institutional IRB.

All events reported to the FDA by the investigator are to be filed utilizing the Form FDA 3500A (MedWatch Form).

To ensure patient safety, every SAE, regardless of suspected causality, occurring

- after the patient has provided informed consent and until at least 30 days after the patient has stopped study treatment/participation
- after protocol-specified procedures begin (e.g., placebo run-in, washout period, double-blind treatment, etc.) and 30 days after the patient has stopped study treatment
- after the start of any period in which the study protocol interferes with the standard medical treatment given to a patient (e.g., treatment withdrawal during washout period, change in treatment to a fixed dose of concomitant medication) and until 30 days after the patient has stopped study treatment

must be reported to The Methodist hospital research Institute and The Methodist hospital Cancer Center within 24 hours of learning of its occurrence (**[contact]**). This includes serious, related, labeled (expected) and serious, related, unlabeled (unexpected) adverse experiences. All deaths during treatment or within 30 days following completion of active protocol therapy must be reported within 5 working days.

Any SAEs experienced after this 30 days period should only be reported to TMHS and TMHCC if the investigator suspects a causal relationship to the study drug. Recurrent episodes, complications, or progression of the initial SAE must be reported as follow-up to the original episode within 24 hours of the investigator receiving the follow-up information. A SAE occurring at a different time interval or otherwise considered completely unrelated to a previously reported one should be reported separately as a new event. The end date of the first event must be provided.

The original copy of the SAE Report and the fax confirmation sheet must be kept within the Trial Master File at the study site.

Follow-up information is sent to the same fax number as the original SAE Report Form was sent, using a new fax cover sheet, stating that this is a follow-up to the previously reported SAE, and giving the date of the original report. Each re-occurrence, complication, or progression of the original event should be

reported as a follow-up to that event regardless of when it occurs. The follow-up information should describe whether the event has resolved or continues, if and how it was treated, whether the blind was broken or not (if applicable), and whether the patient continued or withdrew from study participation.

If the SAE is not previously documented in the Hydroxytyrosol Investigator Brochure or Package Insert (new occurrence) and is thought to be related to the study drug, may urgently require further information from the investigator for Health Authority reporting. TMHCC and TMHRI may need to issue an Investigator Notification (IN), to inform all investigators involved in any study with the same drug that this SAE has been reported. Suspected Unexpected Serious Adverse Reactions (SUSARs) will be collected and reported to the competent authorities and relevant ethics committees in accordance with Directive 2001/20/EC or as per national regulatory requirements in participating countries.

For Comparator Drugs/Secondary Suspects (Concomitant Medications), all serious adverse experiences will be forwarded to the comparator drug company by the investigator.

9 Statistical methods

Study Design and Sample Size. This is a single-arm, pilot breast cancer prevention study of hydroxytyrosol in women at increased risk of breast cancer. Our primary study endpoint will be defined as proportion of women who exhibit a 10% absolute reduction in mammographic density at one-year of follow-up (Cuzick JNCI 2011). For each of the post and pre-menopausal group of women, we will assume under the null hypothesis that 25% of women will exhibit a response (at least a 25% reduction from baseline) versus an alternative hypothesis equal to 45% based on data presented from Cuzick (JNCI 2011). Under these assumptions, a sample of 50 pre-menopausal and 50 post-menopausal women will provide 85% power based on a two-sided test for a single proportion with 5% significance level for each group of women.

Statistical Analysis. Demographics and pre-treatment characteristics will be summarized for 50 premenopausal & 50 postmenopausal women using descriptive statistics. Mammographic density levels at baseline and follow-up time-points as well as categorized levels based on BIRAD criteria will also be summarized using means, standard deviations and proportions. Change from baseline levels of breast density will be analyzed using paired tests while the proportion of women who exhibit at least a 10% absolute reduction from baseline will be calculated along with 95% binomial confidence intervals for each group of women.

Correlative endpoints including Ki-67, apoptosis, Wnt signaling and stem cell pathway markers will likewise be summarized descriptively at each time point of follow-up. Correlations between these markers and with mammographic density levels will be assessed using Spearman or Pearson's correlation coefficients. Change from baseline levels will be analyzed using paired t-test or Wilcoxon-signed rank test.

Multivariate analysis to adjust for demographic/clinical characteristics, specifically age or menopausal status (pre, peri, and post) will likewise be considered using logistic regression for analyzing proportion of women with response or using linear regression models for analysis of quantitative levels of mammographic density. Given the pilot nature of this study, these multivariate analyses will be considered exploratory.

Expected outcome: We expect a decrease in apoptosis, cell proliferation, in post-treatment breast tissue in comparison to pre-treatment. Our previous data reveal an inhibition of Wnt signaling by HT, thus we expect a change in this signaling in this prevention study.

Potential pitfalls, and resolutions: If we do not have enough breast tissue for all determinations, it will be difficult to measure mRNA levels. In such a scenario, we can determine the expression of Sfrp proteins only by multiplex nucleic acid *in situ* hybridization technology (RNAscope) in paraffin embedded tissue slides.

CONFIDENTIAL

10 References:

1. Siegel, R., D. Naishadham, and A. Jemal, Cancer statistics, 2012. *CA Cancer J Clin.* 62(1): p. 10-29.
2. Anderson, D.E., Genetic study of breast cancer: identification of a high risk group. *Cancer*, 1974. 34(4): p. 1090-7.
3. Jatoi, I. and A.B. Miller, Why is breast-cancer mortality declining? *Lancet Oncol.* 2003. 4(4): p. 251-4.

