2.1 Methodology

The mammographic density will be classified by two different methods. Firstly, according to the American College of Radiology's Breast Imaging—Reporting and Data System (BIRADS), and secondly, by using the Cumulus software package developed by the Ontario Cancer Institute to assess percent density as a continuous measure (0-100% scale). The mammograms will be read for research purposes only. They will be read for clinical purposes at the time of the mammogram. The mammograms will be independently reviewed by two radiologists specializing in breast imaging. Quantitative classification of mammographic parenchyma will be based on radiological assessment after digitizing mammograms and measuring percentage density[28, 31].

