4.1 Description of study design

A PILOT STUDY OF HYDROXYTYROSOL, A COMPONENT OF OLIVE OIL FOR BREAST CANCER PREVENTION IN WOMEN AT HIGH RISK OF BREAST CANCER

One hundred (100) pre and post-menopausal women at high risk of breast cancer who have declined tamoxifen, raloxifene or aromatase inhibitor (standard of care) will receive 25mg HT. Eligible women will have a 5 yr risk by Gail Model ≥ 1.7 , or 10% probability of BRCA mutation by BRCAPRO or similar model, or have a previous breast biopsy showing LCIS, atypical lobular or ductal hyperplasia, or have a known germline mutation in *BRCA1* or *BRCA2*. Patients with unilateral breast cancer 5 or more years prior to registration are also allowed. The main exclusion criteria include women who are pregnant or breast feeding, with diagnosis of any malignant disease, or with inability to take oral medication. The women will undergo a mammogram as well as a biopsy of normal breast tissue before and after taking study drug. This biopsy will be directed to the upper outer quadrant, which is typically a dense region. The primary endpoint of this study is change in mammographic density after treatment with HT. The Secondary endpoint will assess toxicity, apoptosis (Fas receptor, cleaved caspase-3, caspase-8, cytochrome c) and cell proliferation (Ki 67 staining, Cdkn2a tumor suppressor, cyclin D1), enzymes related to oxidative stress (ROS and related enzymes), DNA damage by immunohistochemistry, stem cell markers (CD44, CD24, and ALDH), and affection of Wnt signaling (LRP6, β -catenin, Sfrp proteins 1 to 5, DKK1, c-jun, c-myc) before and after drug therapy. If patients undergo a breast MRI before and/or after the completion of the drug, the images will be collected. The study drug will be supplied by PLThomas & Co.. The patients will have a study visit at 3, 6 and 12 months. The study visit will include a general history and physical exam, an assessment for safety and concomitant medications and pill

count. After completion of therapy, the patient will undergo a mammogram as well as a second breast biopsy.

5 Study Population

Each of the criteria in the following section must be met in order for a participant to be considered eligible for registration.

Study Duration:

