5. Participants must have a baseline mammogram performed within 90 days prior to study entry, done on a digital mammography machine that shows either normal or benign findings. Participants with mammograms that are reported as suspicious for malignancy are eligible as long as the biopsy is negative.
6. Participants must have baseline mammographic density $> 10\%$ based upon the classification system (2 = 11-50%, "scattered fibroglandular densities"; 3 = 51-75%, "heterogeneously dense"; 4 = $>75\%$, "extremely dense"). Women with a baseline mammographic density of $\leq 10\%$ (1 = $\leq 10\%$, breasts are almost entirely fat) will not be eligible. Women with a BIRADS score of 4 will be considered eligible as long as the biopsy is benign.
7. Prior tamoxifen, raloxifene or aromatase inhibitor use is allowed provided treatment is completed at least 1 year prior to registration.
8. Participants must not have bilateral breast implants, but prior breast reduction surgery is allowed. (Breast implants are not allowed as they affect density measurements and because of the risk of rupturing the implant with biopsy).
9. Participants must have a ECOG Performance Status of 0 – 1 (see Section 11).
10. Prior anticoagulant therapy use is allowed provided therapy is discontinued at least 7 days prior to the breast biopsy in order to reduce the risk of bleeding. For subjects who have taken an anticoagulation within the past 7 days, INR (International Normalized Ratio) must be $\leq 1.5 \times$ institutional upper limit of normal and Prothrombin Time and Partial Thromboplastin Time \leq IULN prior to the breast biopsy.
11. No prior malignancy is allowed within the past five years except for the following: adequately treated skin cancer and *in situ* cervical cancer .

12. Participant must not be pregnant or nursing and must agree to use effective contraception. Hormone-based birth control (pills, patches or shots) are allowed, but switching birth control methods is discouraged while on-study as hormonal changes can affect mammographic density. Hormone replacement therapy is not allowed for post-menopausal female.
13. Individuals must not participate in any other clinical trial for the treatment or prevention of cancer unless they are no longer receiving the intervention and are in the follow-up phase only. Participants must also agree not to join such a trial while participating in this study.

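### The sentence that sets the 25% null and 45% alternative defines response as a 25% reduction, but the endpoint and the analysis use a 10% absolute reduction, so the benchmark and the power are not tied to the analysed endpoint

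*Combined protocol and SAP*

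**What the plan says.** All the relevant design statements are in Section 9, in consecutive sentences.

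- **Endpoint.** The primary endpoint is the "proportion of women who exhibit a 10% absolute reduction in mammographic density at one-year of follow-up".
- **Rates.** The next sentence sets the hypotheses for each menopausal group: "we will assume under the null hypothesis that 25% of women will exhibit a response (at least a 25% reduction from baseline". The alternative is 45%. The endpoint and the rates cite the same 2011 paper, but no figures from it are reproduced.
- **Sample size.** The sentence after that rests on those assumptions. It says that 50 pre-menopausal and 50 post-menopausal women "will provide 85% power based on a two-sided test for a single proportion with 5% significance level".
- **Analysis.** Under Statistical Analysis, "the proportion of women who exhibit at least a 10% absolute reduction from baseline will be calculated", and the result is reported by group with 95% binomial confidence intervals.

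Elsewhere, Section 2.1 says software will be used "to assess percent density as a continuous measure (0-100% scale", and inclusion criterion 6 in Section 5.1 admits women with baseline density above 10%. Section 4.1 says "The primary endpoint of this study is change in mammographic density after treatment with HT", with no responder threshold. The primary objective in Section 3 gives no threshold either.

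**The concern.** Two responder rules stand side by side. One belongs to the endpoint and the analysis. The other is attached to the null and alternative rates, and through them to the sample size and power. The second does not say whether its 25% is relative or absolute, and no passage links the two.

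The trial has no control arm, so the observed responder proportion can be judged only against the 25% null. If 25% and 45% are rates for a 25% reduction, they are not the rates for a 10-point reduction. The hurdle could then be too high or too low for the endpoint analysed, and the stated 85% power would not apply to it. If the parenthesis merely repeats the 25% null rate by mistake, the rates and power stand. A reader cannot tell which from the text.

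**Working it through.** **Inputs from the documents.** Section 9: null rate 0.25, alternative 0.45, n = 50 per group, two-sided 5% test of a single proportion, power 85%. Section 2.1: density on a 0–100% scale, so a 10% absolute reduction is read as 10 percentage points. Section 5.1: baseline density above 10%.

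**1. Reproduce the stated power.** Arcsine formula:

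h = 2·asin(√0.45) − 2·asin(√0.25) = 0.4234

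Power = Φ(h·√50 − 1.96) = Φ(2.994 − 1.960) = Φ(1.034) = 84.9%

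The stated 85% follows from 25% against 45%. The normal approximation with null variance and continuity correction gives 84.0%. An exact binomial rule gives 80.3% (step 3). The arithmetic is not at fault.

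**2. Compare the two rules.**

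*If the 25% is absolute*, it is 25 points against 10. A woman with baseline density of 11–24% is eligible and can lose 10 points, but cannot lose 25.

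*If it is relative*, a 10-point fall is 10/b of baseline b, and a 25% fall is 0.25·b points:

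| Baseline b | 10 points as % of b | 25% of b, in points |
|---|---|---|
| 11% | 91% | 2.75 |
| 20% | 50% | 5 |
| 40% | 25% | 10 |
| 80% | 12.5% | 20 |

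The rules coincide only at 40%. Below that the 10-point rule is stricter; above it the 10-point rule is easier. The same woman can respond on one rule and not on the other.

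**3. What a misplaced null would do.** Section 9 does not name the type of binomial interval. I take the exact (Clopper-Pearson) 95% interval as an assumption. Its lower limit is 24.7% at 19/50 and 26.4% at 20/50, so at least 20 of 50 responders are needed to exclude 25%. With X ~ Bin(50, p):

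| True 10-point rate p | P(X ≥ 20) |
|---|---|
| 20% | 0.1% |
| 25% | 1.4% |
| 30% | 8.5% |
| 35% | 27.4% |
| 45% | 80.3% |

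Read as no-effect rates, the 20%, 30% and 35% rows show how far the false-success rate moves if the real null is not 25%.

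**4. Illustration of the direction of error (all assumed).** The documents give no SD of change and no baseline distribution. Take the relative reading, a normally distributed change, and uniform baselines. Choose the SD so that the no-effect rate on the 25% relative rule is 25%, that is, the mean of Φ(−0.25b/SD) over the baselines is 0.25. The 10-point rate is then Φ(−10/SD). For the alternative, shift the mean change until the relative rate is 45% and recompute the 10-point rate.

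| Baseline range | SD | No-effect 10-point rate | P(X ≥ 20) | Mean change at 45% relative | 10-point rate | P(X ≥ 20) |
|---|---|---|---|---|---|---|
| 11–30% | 7.5 | 9% | near 0 | −4.2 | 22% | 0.3% |
| 11–90% | 17.8 | 29% | 5.7% | −10.3 | 51% | 95% |
| 51–90% | 26.0 | 35% | 27% | −14.3 | 57% | 99% |

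The error can go either way, depending on who is enrolled. The SD of 26 is large: before truncation that model puts about 15% of follow-up densities above 100%. Truncating follow-up density to 0–100 leaves the no-effect 10-point rates unchanged (0.090 for 11–30%, 0.349 for 51–90%).

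**The case against.** The text leans towards a slip. The endpoint and analysis sentences both say 10% absolute. The word for response follows directly on the endpoint just defined, both sentences cite one paper, and the parenthesis repeats a figure given a few words earlier. If so, no design figure is wrong. This is plausible, but the parenthesis also reads as a complete definition, and a shared citation does not show which definition the rates describe.

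The study is a pilot, it also plans paired tests of change that do not use the 25% null, and the analysis paragraph states no success rule tied to that null. This is true and limits the damage. Section 9 nevertheless specifies a powered two-sided test against 25% for this endpoint, and labels only the multivariate analyses exploratory.

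The 20/50 threshold depends on the exact interval. At 19/50 the z statistic with null variance is 2.12, the exact minimum-likelihood p-value is 0.048 and the Wilson lower limit is 25.9%, so each of these excludes 25%. On that rule the chance of success is 2.9% at a true 25% and 87% at 45%. This stands as a caveat on the size of the figures. It does not touch the conflict between definitions.

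The illustration rests on assumed distributions and does not bound the real error. Two of its three alternatives need mean falls above 10 points, whereas Section 2 quotes up to 4.3% yearly for tamoxifen. It shows direction only, and the finding does not depend on it.

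**Conclusion.** The concern holds. Section 9 attaches its null and alternative rates to a different responder rule from the one it names as the endpoint and analyses. The rules differ on every reading except a relative one at 40% baseline density.

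The 85% is correctly computed from 25% and 45%; what is not shown is that those rates belong to the 10-point endpoint. No single corrected power can be given, because the documents contain no separate 10-point rates. If the parenthesis is a slip, the power stays at 85% (arcsine) or 80.3% (exact rule). If it is not, both the benchmark and the power for the analysed endpoint are unknown, with consequences of the order shown under the stated assumptions. The point should be settled before analysis because it concerns the primary responder definition and its only benchmark.

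**What to change.** 1. Check in the cited source which response definition the 25% and 45% describe. Do this before editing, because the parenthesis may be the only trace of their origin.
2. Use one definition in Section 9: a fall of at least 10 percentage points in percent density at one year. The endpoint and analysis sentences already have this threshold. Delete the parenthesis with the 25% reduction.
3. State that response is measured on the continuous 0–100% scale of Section 2.1, which Section 9 does not name. Refer to this definition in Section 4.1 and, for consistency, in the primary objective in Section 3.
4. If the source rates belong to another definition, replace them with rates for the 10-point rule and restate the power for 50 women per group.

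The cost is a few lines of text and one look at the source, with no added patients or procedures. New rates and a restated power are needed only if step 1 calls for them.
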